2.2 Investigational Product

Xylitol (E967) and erythritol (E968) are sweeteners naturally found in low concentrations in fruits and vegetables, and can be extracted from fibrous material such as birch and used as natural sugar replacers. Since the 1970ies beneficial effects on oral health could be demonstrated as oral microbiota is influenced positively with reduction of Streptococcus mutans, as an example⁹. Interest now arises because of multiple potential health benefits that have been observed in studies examining polyols: apart from being non-cariogenic they are low glycaemic, low-energy and low-insulinaemic, and low-digestable and seem to act as hydroxyl radical scavenger¹⁰. In rats, xylitol consumption suppressed high-fat induced visceral fat accumulation¹¹, improved islet cell morphology¹² and lead to amelioration of glycaemic control¹³. Results from our own research show deceleration of gastric emptying and a marked increase in GLP-1 and CCK after xylitol and erythritol consumption¹⁵. Stimulation of incretin release might in part be responsible for amelioration of glycaemic control.

2.3 Dose Rationale

- 1) Tolerance: Previous trials have been carried out with polyol doses up to 200g per day, however if 50g or more per day are consumed, the risk of gastrointestinal discomfort increases.
- 2) Previous metabolic effects: A pilot trial by Flint et al. could show metabolic effects after 4 weeks of 36g of erythritol consumption in that vascular function improved²⁰.
- 3) Average sugar consumption: Average daily sugar consumption in Switzerland is estimated to be ca. 120g of sucrose/d. Of these 120g an estimated 80% is consumed as "hidden sugars" and 20% as table sugar, which corresponds to ca. 24g of table sugar/d. Should the above mentioned dosage of natural sweeteners show positive metabolic effects, it seems a feasible dosage to replace daily direct sucrose intake. Xylitol is given in a dosage equisweet to erythritol.

2.4 Explanation for choice of comparator

We intend to use a control-group to compare effects. Unfortunately, a placebo-controlled study design is not possible in this case: a placebo would have to be approximately equisweet without any known metabolic effects. However, there are no such substances: artificial sweeteners such as e.g. aspartame are much sweeter and it would be impossible to keep the blinding. Apart from that, artificial sweeteners probably have metabolic side-effects and are not inert. All carbohydrates have some metabolic effects themselves. We accept the possible placebo-effect of the two polyols. However, participants will serve

as their own controls (before-after treatment) as well.

2.5 Risks / Benefits

Participants do not profit directly from this study. However, in the long term, findings could lead to a new nutritional concept in obese patients. In sensitive subjects consumption of polyols can lead to borborygmi and diarrhoea. However, if the amount of polyols is distributed over the day - as planned we do not expect intake to cause discomfort. To gain peripheral venous access can be challenging in morbidly obese subjects. Occasionally, blood sampling can result in local skin irritation, hematoma and discomfort. However, well-trained study personnel (used to this special population) will place venous accesses and collect blood samples.

Justification of choice of study population 2.6

In this trial, obese but otherwise healthy volunteers will be included. In morbid obesity virtually all patients suffer from metabolic syndrome with non-alcoholic fatty liver disease, dyslipidaemia and impaired glucose tolerance. In animal models, xylitol consumption led to decrease in visceral fat¹¹ and metabolic syndrome. In a human study carried out on lean subjects in 1982, 3 weeks of xylitol intake showed a decrease in plasma cholesterol values¹⁴.

3. STUDY OBJECTIVES

Overall Objective

The purpose of this study is to evaluate whether daily intake of erythritol or xylitol over a period of 7 weeks will alter gut microbiota composition and glucose tolerance.

3.2 Primary Objective

Glycaemic control (fasting insulin & glucose & c-peptide after oral glucose challenge)

3.3 Secondary Objectives

- Human gut microbiota composition
- Metabolomics
- Blood lipids, hepatic enzymes
- Inflammatory response
- Intestinal permeability
- Gastrointestinal tolerance (bloating, diarrhoea etc.)
- Intestinal glucose absorption

Safety Objectives

The study also aims to assess tolerability in terms of incidence of gastrointestinal side effects of the two polyols.

4. STUDY OUTCOMES

4.1 Primary Outcome

Glycemic control: Before and after treatment, an oral glucose tolerance test will be carried out. In this trial, we will include more time-points (0-30-60-90-120min. after glucose ingestion) for an accurate assessment of pharmacokinetics (AUC: area under the curve, Cmax, Tmax).

STANDARD ORAL GLUCOSE TOLERANCE TEST: DEFINITIONS

Diabetes: Fasting plasma glucose ≥7.0mmol/l or ≥11.1mmol/l (OGGT: 2-h plasma glucose))

Impaired Glucose Tolerance (IGT): Fasting plasma glucose <7.0mmol/l and ≥7.8 and <11.1mmol/l (OGGT: 2-h plasma glucose)

Impaired Fasting Glucose (IFG): Fasting plasma glucose 6.1 to 6.9mmol/l and <7.8mmol/l (OGGT: 2-h plasma glucose).

Definition and Diagnosis of Diabetes Mellitus and Intermediate Hyperglycaemia: Report of a WHO/IDF consultation. World Health Organization 2006

4.2 Secondary Outcomes

- Human gut microbiota composition: Faecal samples will be taken before and after treatment and the taxonomic and functional profiles of the gut microbiota will be assessed by metagenomic shotgun sequencing.
- Metabolomics: Faecal and urine samples will be used for analysis of the metabolome using metabolomics.
- Blood lipid profile, hsCRP and hepatic enzymes: Fasting samples will be taken to measure triglyceride, total cholesterol, LDL and HDL levels, and the liver enzymes ASAT (aspartate transaminase) and ALAT (alanine transaminase). The analysis will be carried out in the hospital laboratory (St. Claraspital).
- **Inflammatory response:** As erythritol might act as a radical scavenger and reduce oxidative stress, we plan to assess inflammatory state by measuring IL-6, TNF-α, sTNFR1, sTNFR2, high sensitive CRP (hsCRP) and leucocytes.
- Intestinal permeability: Circulating markers of intestinal permeability (zonulin, LPS) will be measured.
- Gastrointestinal tolerance (bloating, diarrhoea etc.): We will assess gastrointestinal symptoms by using a validated questionnaire (Clinical rating scale for gastrointestinal symptoms: Svedlund et al.²¹). The questionnaire will be used at baseline and at the end of week 3 and 7 (self-reporting). A license agreement will be sent to AstraZeneca (ASTRAZENECA AB, 556011-7482 S-151 85 Södertälje, Sweden).
- 4.3 Intestinal Glucoseabsorption: We will assess intestinal glucose absorption by use of a validated technique: during the oral glucose tolerance test, 3g of 3-O-Methyl-Glucose (3-OMG) is ingested. 3-OMG is then measured in the plasma samples obtained at 0-30-60-90-120min. Other Outcomes of Interest

We accept that a possible confounder might be the substitution of sucrose in daily life as polyols might serve as a substitute. If sugar consumption is reduced, metabolic effects could be caused by reduced sugar exposure rather than polyol intake. We will therefore assess overall sugar consumption before and during the trial. Participants will keep a food diary. For this purpose we will use the clinical diary used by our nutritionists for preoperative assessment of bariatric patients.

4.4 Safety Outcomes

Gastrointestinal tolerance (bloating, diarrhoea etc.): Incidence and severity of gastrointestinal side effects related to the sweetener intake during the study is assessed by using a questionnaire (Clinical rating scale for gastrointestinal symptoms: Svedlund et al.²¹)

5. STUDY DESIGN

5.1 General study design and justification of design

This pilot trial is a randomized, controlled interventional study; the project set-up will be single-centre, national. Participants will be randomized to one of the three groups: control-group (1), xylitol group (2) or erythritol group (3). They will then get pre-portioned sticks of either xylitol (24g/d; 3x8g) or erythritol (36g/d; 3x12g) or no food supplement (control-group). During the whole period patients will keep a food diary, where they will also report intake of sweeteners and once a week they will fill in a clinical gastrointestinal symptoms questionnaire. The food diary and gastrointestinal symptoms questionnaire will be sent to the clinical trial unit once a week. Once every week volunteers will receive a phone call by the study nurse in order to make sure the sweetener is well-tolerated, compliance is guaranteed and no adverse events occur. At baseline and after 7 weeks, patients will be examined: a) metabolic work-up: oral glucose tolerance test, liver enzymes, blood lipids, b) biomarkers of gastrointestinal permeability and inflammatory response, c) urine and faecal samples (metabolomics), and d) faecal sampling (gut microbiota composition). Upon conclusion of the study, remaining sweetener sticks and questionnaires are returned.

Demographic and personal data (year of birth, weight, height, age, gender, abdominal circumference, blood pressure, medical history) will be saved in a computer database.

Participant recruitment will be achieved through referring physicians from the Ernährungszentrum St. Claraspital, where morbidly obese patients are seen in an outpatient setting before bariatric surgery and are usually on a rather long waiting list before surgery. In case patients are interested in participating,

Effect of the natural sweeteners erythritol and xylitol on vascular function in obese volunteers:

A pilot study, Version 1, 11.4.2016, Version 2, 6.6.2016, Version 3, 25.9.2017

they will be contacted by the principal investigator ([name] [name]) or the study nurse ([name]) and a screening appointment will be made.

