Gastrointestinal symptoms will be assessed by use of a validated questionnaire (Clinical rating scale for gastrointestinal symptoms: Svedlund et al., 21). The questionnaire will be used at baseline and at the end of week 3 and 7 (self-reporting). A license agreement will be sent to AstraZeneca (ASTRAZENECA AB, 556011-7482 S-151 85 Södertälje, Sweden). The GSRS is a disease-specific instrument, developed based on reviews of gastrointestinal symptoms and clinical experience, to evaluate common symptoms of gastrointestinal disorders. ^{21,23} The GSRS contains 15 items, each rated on a seven-point Likert scale from no discomfort to very severe discomfort. Based on a factor analysis, the 15 GSRS items break down into the following five scales: abdominal pain (abdominal pain, hunger pains and nausea); reflux syndrome (heartburn and acid regurgitation), diarrhoea syndrome (diarrhoea, loose stools and urgent need for defecation), indigestion syndrome (borborygmus, abdominal distension, eructation and increased flatus) and constipation syndrome (constipation, hard stools and feeling of incomplete evacuation).²³ The scores are calculated by taking the mean of the items completed within an individual scale, with higher scores indicating greater severity of symptoms. The GSRS in European patient populations has a good internal consistency reliability and acceptable construct validity and responsiveness.²³⁻²⁵ The GSRS can be administered in either self-report or interview format.

Intestinal Glucoseabsorption: We will assess intestinal glucose absorption by use of a validated technique ^{26,27}. During the oral glucose tolerance test, 3g of 3-O-Methyl-Glucose (3-OMG) is ingested. 3-OMG is then measured in the plasma samples obtained at 0-30-60-90-120min by means of high performance exchange chromatography.

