8.3.2 Second Visit = 1. Metabolic Visit

The **second visit (1. metabolic visit)** at our outpatient clinic will take about 2.5 hours. We will carry out an oral glucose tolerance test and take blood, and urine samples. If possible, the participant will bring the first faecal sample to this visit. Again, the participant has to arrive on an empty stomach (not allowed to eat or drink 10 hours prior to this appointment except for tap water or unsweetened herbal tea without milk). Even chewing gum must be avoided, as they might contain sugar. In addition 2 days prior to the test the participant has to refrain from heavy physical activity and needs to have carbohydrates as part of her/his meals.

- The candidate will be assigned randomly to one of the three groups (intake of xylitol, or erythritol or control group).
- The participant needs to bring his/her study folder along, including the food diary which he/she should have kept over the course of 1 week.
- If possible, the participant will bring along the first faecal sample
- We will take a first blood sample to measure blood sugar, insulin, C-peptide (for the oral glucose tolerance test). In addition we will measure biomarkers of inflammatory response (IL-6, TNF- α, sTNFR1, sTNFR2) and intestinal permeability (zonulin and LPS).
- The participant will receive 75 g of glucose (grape sugar) plus 3g 3-O-Methyl-D-glucose dissolved in 300mL tap water which he/she will have to drink over a period of 5-10min. ("oral glucose tolerance test")
- After 30, 60, 90 and 120min we will again take blood samples for measurement of blood sugar, insulin, C-peptide and 3-OMG. In total we will take a maximum of 30mL blood (corresponding to 3 tablespoons).
- During this appointment we will fill in the questionnaire for gastrointestinal symptoms together with the participant.
- At the end of the visit, the participant will receive the portioned sweeteners (if assigned to one of the polyol groups) and the kit for the second faecal sample.

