Oral glucose tolerance test 75g glucose (0-30- 60-90-120min)		х								х
Blood glucose		х	-							х
Insulin		х	1							х
C-peptide		х	ses:							Х
3-O-Methyl-D-Glucose		х	j op r							Х
Urine sample		х	3.50) -0.0) -1-0)							Х
Faecal sample		х	n (1-C ns (1-C							Х
GSRS: questionnaire gastrointestinal symptoms	х		Adaption week with increasing doses: • 2 days 1 portion (1-0-0) • 3 days 2 portions (1-1-0) • 2 days 3 portions (1-1-1)		х				х	
Food diary		х	reek days days days		х				х	
Follow-up calls			0 N N	х	х	х	х	х	х	
SAE			laptio	х	х	х	х	х	х	Х
End of study meeting			PΑ							х

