10.4 Planned Analyses

10.4.1 Datasets to be analysed, analysis populations

In this pilot trial which is purely observational, an analysis per protocol is planned. Drop-outs will be replaced, but baseline data of drop-outs might be included to characterize the baseline population. Baseline values of all three groups will be compared, to rule out any baseline differences. The control group will also be examined twice, and the two time-points should yield similar results. Data from each participant before and after treatment will be analyzed in the sweetener groups. In that way, each participant will serve as his or her own control. Post-treatment values of both treatment groups will then be compared to the control group (without treatment).

In case both sweeteners should have an effect on our endpoints, we might combine the two arms for an additional analysis comparing "no sweetener" (n= 20) vs. "sweetener" (n= 40).

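### The GSRS is weekly in section 5.1 but only at baseline, week 3 and week 7 elsewhere, and its baseline visit and mode of completion also conflict

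*Protocol*

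**What the plan says.** **Frequency.** Protocol section 5.1, describing the whole study period, says that "once a week they will fill in a clinical gastrointestinal symptoms questionnaire" and adds: "The food diary and gastrointestinal symptoms questionnaire will be sent to the clinical trial unit once a week". Section 8.2.2, in a sentence that also stands in 4.2, has: "The questionnaire will be used at baseline and at the end of week 3 and 7 (self-reporting"). Both copies of the schedule of assessments carry a row "GSRS: questionnaire gastrointestinal symptoms" with ticks at V1 (screening, day -7), week 3 and week 7, and none at V2 or V3.

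**Baseline visit and mode.** Section 8.3.2 puts a form at V2: "we will fill in the questionnaire for gastrointestinal symptoms together with the participant". Random assignment takes place at that same visit. Section 8.2.2 also states that the scale may be given by self-report or by interview.

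**Use.** Section 4.4 reads: "Incidence and severity of gastrointestinal side effects related to the sweetener intake during the study is assessed by using a questionnaire". The safety objective in section 3 is the incidence of gastrointestinal side effects of the two polyols. Section 10.4.1 plans a per-protocol analysis and says: "Drop-outs will be replaced".

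**The concern.** Staff cannot follow both versions of the schedule, and the choice decides what the safety outcome can show. The first week is a step-up period meant to let the gut adapt, so the protocol itself treats the early days as the sensitive ones. With forms only at weeks 3 and 7, the instrument named for incidence and severity does not cover the adaption week or week 2. Its scores then come only from people who have tolerated the product for three weeks.

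The unclear baseline adds a second problem. The main planned contrast in the sweetener groups is before versus after within a participant. If the baseline form is completed with staff and the later forms alone, part of any change may reflect how the form was filled in.

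**Working it through.** The plan gives no figure to reproduce. The check sets the passages side by side and counts forms and days.

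**1. Same instrument?** Section 5.1 does not use the name GSRS. The appendices list only one gastrointestinal form in the study folder, the GSRS, so 5.1, 4.2 and 8.2.2 describe the same questionnaire.

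**2. On-treatment forms per participant.**
- Section 5.1: 7 weeks x 1 per week = 7.
- Sections 4.2 and 8.2.2 and both schedule tables: weeks 3 and 7 = 2.
- Difference: 7 - 2 = 5.

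**3. First on-treatment score under the week 3/7 version.** The end of week 3 is 3 x 7 = day 21. Section 7.2.1 gives one portion on days 1 to 2, two portions on days 3 to 5, and three portions from day 6. By day 21 a participant has had 21 - 6 + 1 = 16 days on three portions. The complete step-up lies before the first score.

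**4. A participant who stops for intolerance before day 21.**
- Section 7.3: poor gastrointestinal tolerance leads to discontinuation.
- Section 8.2.5: no follow-up visit after discontinuation.
- Sections 6.4 and 7.5: data already collected are kept. Under the week 3/7 version there is no on-treatment GSRS score to keep.
- Section 10.4.1: per-protocol analysis, with the drop-out replaced.

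The person who tolerated the product worst leaves the GSRS data and another person takes the place. This removal depends on the outcome itself, so incidence and severity based on the GSRS would tend to be too low in the polyol arms. Under section 5.1 the same person would have a form for each completed week, and sections 6.4 and 7.5 would keep it.

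**5. Baseline.** The schedule ticks V1 and leaves V2 empty, while 8.3.2 has the form at V2. Section 5.2.2 says that the investigator and the study nurse are not blinded. Section 8.3.2 lists random assignment as its first item but fixes no order, so the form could be completed before or after the group is known. A form at V1 would precede randomisation.

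**6. Mode.** There are two readings. If the bracketed remark on self-report in 4.2 and 8.2.2 covers baseline, those sections contradict 8.3.2. If it covers only weeks 3 and 7, the mode changes between baseline and follow-up. Write d for a shift due to mode. Within a group, observed change = true change + d. Between groups, (change in polyol arm + d) - (change in control arm + d) = difference in true change, provided d is the same in each arm. The documents give no size or direction for d.

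**The case against.** The strongest reply is that tolerability does not rest on the GSRS alone. Section 5.1 has weekly calls to check tolerance, 8.2.4 has participants report undesired effects directly, 8.2.4.1 asks them to report any symptom, section 9 collects all adverse events throughout, and 10.4.5 compares them between groups. Intolerable gastrointestinal effects are also a named withdrawal reason in 6.4. All of this stands. A reader might infer that the GSRS is the only measure of the safety objective, or that early intolerance goes unmeasured. The documents do not support either reading.

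What remains is narrower. Section 4.4 assigns incidence and severity to the questionnaire, and 8.2.4.1 relies on it for gastrointestinal symptoms. Section 9 defines seriousness and causality but sets no severity grading. Adverse-event reports also pass through unblinded staff from participants who know whether they receive a sweetener. Adverse-event data are therefore a partial substitute for the missing scores.

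Three further objections have force.
- **Mode.** A reader might infer a settled mixed-mode design that biases every comparison. The text shows a conflict of wording, both formats are allowed, and a common shift would cancel against control. The problem is confined to the before-after change, and arises only if 8.3.2 is followed.
- **Week 1 calls.** The schedule as extracted ticks calls only from week 2, but the week 1 cell is filled by the adaption text. No gap in calls can be inferred.
- **Weekly forms are not complete cover.** Someone who stops on day 3 completes no end-of-week form either. For that reason adverse events and discontinuations must be counted as well.

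Finally, a definition of incidence may stand in the statistical analysis plan, which is not shown. The contradiction over which forms are collected is in the protocol and has to be settled there.

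**Conclusion.** The contradiction is real and unresolved in current text: 7 on-treatment GSRS forms in section 5.1 against 2 in sections 4.2 and 8.2.2 and both schedule tables, with two baseline visits and two modes.

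The consequences are conditional. If the week 3/7 version applies, the GSRS gives no on-treatment score before day 21, and GSRS-based incidence and severity would tend to be understated because early intolerant participants are replaced. If 8.3.2 applies at baseline, the within-group change mixes assisted and self-completed forms.

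The size of the understatement cannot be given. The protocol states no drop-out rate, and section 2.5 expects no discomfort from divided intake. Any percentage of exposed participants lost would rest on an assumed number of early stops. The point concerns a safety and secondary outcome and leaves the primary outcome untouched.

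**What to change.** - Reconcile sections 4.2, 5.1, 8.2.2 and 8.3.2 and both schedule tables to one GSRS schedule, the same in all three arms. The weekly form is preferable, because 5.1 already foresees it and it reaches the adaption week.
- Name one baseline visit and one mode: a self-completed form, finished before the group is disclosed.
- Report gastrointestinal tolerability for all randomised participants, including those who stop and are replaced, from three sources together: GSRS scores, gastrointestinal adverse events, and discontinuations for intolerance.
- Do not define a case as any worsening on any scale in any week. With 5 scales and 7 weeks there are 35 chances per person. If chance alone worsens 5% to 10% of scale-weeks (an assumption, with independence), 1 - 0.95^35 = 83% to 1 - 0.90^35 = 97% of participants would count as cases, controls included.
- Settle the food diary at the same time. It is kept for the whole period in 5.1 but only in weeks 3 and 7 on treatment in 8.2.3.

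**Cost.** If weekly forms were intended, only the text changes. If weeks 3 and 7 were intended, there are up to five more short forms per participant, or 5 x 60 = 300 for the planned sample, plus those of participants who are replaced.
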